4.3 Expected duration

The total duration of the study, from the first visit of the first patient to the preparation of the final report, is estimated to be 7 months.

The planned recruitment period is 5 months, however, as 1 month of treatment is required, the final recruitment period will be 4 months. Considering that the proposed sample is 141 subjects, the total average recruitment rate during the study should be no less than 1 subject per day. This may vary depending on the number of open centers.

The approximate duration of each subject in the study is up to 34 days.

5. Study population

5.1 Eligibility criteria

5.1.1 Inclusion criteria

- Be of legal age.
- Have the ability to voluntarily give their signed informed consent.
- Be able and willing to comply with scheduled visits, treatment plan, and other study procedures.
- Be willing to modify lifestyle activities.
- Women of childbearing potential must ensure the continuation (initiated ≥ 30 days prior to signing the ICF) of the use of a hormonal contraceptive method or IUD during the study period.
- Have a diagnosis of mild to moderate dry eye, defined by:
 - OSDI from 13 to 32 points
 - + 1 of the following:
 - Corneal staining with more than 5 sites.
 - Conjunctival staining with more than 9 sites.
 - TFRT < 10 seconds.

5.2 Criteria for exclusion and substitution of subjects

5.2.1 Exclusion criteria

- Be pregnant, breastfeeding, or planning to become pregnant within the study period.
- Have participated in another clinical research study ≤ 30 days prior to the scrutiny.
- Have previously participated in this study.
- Have a better corrected visual acuity (BCVA) of 20/200 or worse in one of the eyes.
- Present an ophthalmological diagnosis of:
 - Allergic, viral, or bacterial conjunctivitis.
 - Anterior blepharitis.
 - Parasitic eye infections (e.g., Demodex).
 - Unresolved eye trauma.
 - Healing diseases of the ocular surface.
 - Corneal or conjunctival ulcers.
 - Filamentous keratitis.

- Neurotrophic keratitis.
 - Bullous keratopathy.
 - Neoplastic diseases on the ocular surface or adnexa.
 - Diseases with fibrovascular proliferations on the conjunctival and/or corneal surface.
 - Retinal and/or posterior segment diseases that require treatment or threaten visual prognosis.
 - Glaucoma.
- Have a management of your dry eye that requires the implementation of stage 2 treatments of the TFO DEWS II recommendations in the treatment and staged management for dry eye disease.
 - Have a history of drug addiction or drug dependence current or within the last two years prior to signing the ICF.
 - Have a history of eye surgical procedure within the last 3 months prior to signing the ICF.
 - Be a soft or hard contact lens wearer. You will be able to enter if you can suspend its use during the study, you must complete 15 days without using the contact lens prior to your inclusion.
 - Have another medical condition, acute or chronic, that in the investigator's judgment may increase the risk associated with participation in the study or administration of the investigational product, or that may interfere with the interpretation of the results of the study.
 - Have known hypersensitivity to the components of the investigational products.

5.2.2 Subject substitution

The sponsor, with prior authorization from the Research Ethics Committees (REC), may decide to replace the subjects who withdraw their ICF or those who present loss of follow-up, in case it is necessary to balance the groups of studies so that they are evaluable.

5.3 Lifestyle considerations

For the study, participants may need to modify some lifestyle activities to comply with the following:

- Abstain from tobacco use.

- Refrain from using electronic vaporizers.
- Avoid submerging yourself in water without eye protection (*goggles*).
- Avoid direct exposure to fans (including air conditioning vents) during activities that involve vision. 24 hours before your check-up visits.
- Maintain your sleep-wake cycle with which you enter the study.

5.4 Screening failure

A screening failure is defined as those participants who agree to participate in the study, giving their consent, but who are not assigned to a treatment group, i.e., do not enter the study. It is necessary to report at least the following information on counting failures:

- Demographics.
- Details of the failure to count (specify whether it is due to eligibility criteria, which one, or some other reason for the failure).
- Presence of serious AEs during the count.

This is necessary to comply with the CONSORT (Consolidated Standards for the Publication of Clinical Trials) guidelines for the publication of results or to answer possible questions from regulatory authorities.

Subjects who do not meet the eligibility criteria to participate in the study due to a specific modifiable factor may re-participate in the scrutiny. The subjects in this case must use the same initial count number.

5.5 Recruitment and retention strategies

This is a phase II study, which is planned to be conducted at least 4 centers. The selected centers will be responsible for the recruitment of the subjects.

The minimum expected recruitment rate is 1 subject per day.

The duration of the subject's participation in the study is approximately 33 days, during which time he or she will only have to attend two visits after the initial one. The subjects will be entitled to travel support for transportation and for complying with their visits. Other strategies to improve subject retention include:

- Clearly inform the importance of the study and the benefits that the population will obtain from its results.

6. Investigational product

6.1 Administered product

1. Investigational product

- Generic name: Sodium hyaluronate.
- Distinctive name: Multi-doses Lagricel® Ofteno.
- Active ingredients: Sodium hyaluronate 0.4%.

- 
- Pharmaceutical form: Ophthalmic solution.
 - Presentation: Multi-dose dropper bottle.
 - Prepared by: Laboratorios Sophia, S.A. de C.V.
 - Solution Description: Transparent solution, free of visible particles.
 - Packaging description: White bottle with a capacity of 10 mL, made of low-density polyethylene.

2. Dose of the investigational medicinal product

Three different dosages will be used, each of the groups will use one of the following:

- One drop BID, OU, for 30 days (suggested time between applications is 12 hours).
- One drop QID, OU, for 30 days (minimum time between applications of 3 hours).
- One drop 6x/D, OU, for 30 days (minimum time between applications of 3 hours).

6.1.2.1 Dose Justification

Generally, ophthalmic lubricants are prescribed as needed (*pro re nata* [PRN]). [38] However, the study by Asbell *et al* compared the efficacy of QID dosage against PRN. Their results showed that, although there was no difference in clinical signs, the QID group had greater improvement in symptomatology. [39]

For these reasons, 3 different dosages are proposed for this study, considering that the optimal dosage of IP would be QID.

6.2 Storage and handling of the investigational product at the study center

The delivery will be made by means of a courier service contracted by the sponsor, expressly selected for this purpose, to the address of the research center according to the study plan.

The reception will be carried out by the assigned personnel of the research team. The good condition of the primary packaging (box) must be verified.

In the event that you show alterations or defects in its integrity that in your judgment could have damaged the content, you must report it to the sponsor. If the package does not show significant defects, it will proceed to open it.

Inside, the acknowledgment of receipt document and the temperature *data logger* must be located.

It must be checked that the temperature recorded complies with what is specified for its transport and safekeeping. The content (IP) will be verified with what is reported in the document. In case the document corresponds to the content, you will sign the receipt and send it to the sponsor. Otherwise, the sponsor will be notified.

Storage and safeguarding are the responsibility of the research center. The medication must be stored in a secure area with restricted access.

The storage temperature should be no more than 30°C.

The research center is obliged to record, in the designated format, the temperature recorded in the *data logger*, every day while the protocol is in force and has IPs. These data will be reviewed by the clinical monitor according to the record in the *data logger*.

In the event of loss of material, it must be documented in the logbook of inputs and outputs along with a clear description of the mechanism by which the loss occurred.

Upon completion of the protocol, all study material will be retrieved by the sponsor as part of the closing audit.

The final delivery of material will be made by the principal investigator or the person designated by him to deliver material at the end of the study.

The sponsor reserves the right to initiate civil and criminal action against the principal investigator in the event of a lack of undocumented material at the conclusion of the study.

6.3 Concomitant treatments and medications not authorized during the study

Unauthorized medicines will not be allowed during the intervention period, including the period between the end of BV and D1, from D1 the IP application scheme will begin. The objective of this restriction is to avoid drug interactions that could alter the results of the variables evaluated.

Medications allowed: Ophthalmic: Tetracaine 0.5%, Tropicamide 0.8% / Phenylephrine 5% (for study procedures) and IP. Non-ophthalmic: Hormonal contraceptives. At the discretion of the investigator, systemic medicines whose effects do not modify the efficacy or safety parameters of this protocol may be used, but must be reported to the sponsor's scientific committee to determine the participant's status as appropriate.

Prohibited Drugs: Any ophthalmic drugs that are not on the list of allowed drugs. Systemic medications: steroids, immunomodulators, and tetracyclines.

6.4 Procedure for monitoring and measuring adherence

For more than four decades, research has been conducted on the appropriate way to measure and quantify medication adherence, but none is considered the gold standard in both cross-sectional and longitudinal studies. [40, 41, 42, 43, 44, 45, 46, 47] There are different procedures to measure adherence to pharmacological interventions. The most common procedure is self-reporting, which includes: patient interviews, questionnaires and self-monitoring diaries. Its strengths are speed, flexibility, low cost and ease of implementation; They have a high degree of specificity for non-adherence, but the sensitivity and reliability for adherence is low. [47, 48] The biochemical measurement of the drug, or its metabolite, are methods that better confirm the use of the drug; but it raises costs, is impractical and of little use in ophthalmic applications, since concentrations at the peripheral level could be undetectable; samples of other tissues involve more invasive methods that would not be advisable. [47]

Medication counting is another way to measure adherence. Classically referred to as "pill counting," in ophthalmology it translates to the weight of the bottle. This is a simple, inexpensive, and non-invasive method.

The main disadvantages of this method are:

1. The application of the medication cannot be confirmed (it may have been intentionally pulled or instilled outside the eye)
2. It depends on the subject bringing back the medication. [47, 48]

However, in this study, the initial and final weight of the bottle will also be taken into account to measure adherence, at the same time adherence will be measured through the subject's diary.

A multi-procedure approach to measuring adherence is recommended. Because there is no measurement of ideal adherence, it is appropriate to use more than one method when trying to achieve results that resemble reality. Selecting two or more methods allows their strengths and weaknesses to be compensated, to capture adherence levels more accurately. [46]

The evaluation of adherence will be favored by means of the weight of the bottle and will be carried out in the following way, taking into account the following information: the weight of the drop, the initial weight of the container, the final weight of the container and the calculation of the total applications. The following simplified formula shall be used:

$$Ad = \frac{(P_i - P_f)100}{PT}$$

Where:

Ad = adherence

P_i = weight of the container delivered to the subject at the beginning

P_f = weight of the container returned by the subject

PT = weight of the dosage indicated for the intervention

$$PT = (P_g)G$$

Where:

P_g = weight of one drop of the intervention, determined by the research and development department

G = number of applications indicated for the intervention

Packaging that does not retain its physical integrity will not be considered for the calculation of adherence. In cases where the container is not returned, or it has not preserved its physical integrity, adherence will be measured only through the subject's diary

Adherence through the subject's diary will be measured as follows:

$$Ad = (Ar)100/Ai$$

Ad = Adhesion

Ar = Registered Applications

Ai = Applications indicated for the products under investigation

There is no standardized parameter to define adequate adherence, it must be defined and delineated by the objectives of the particular research. [47]

For this study, a minimum adherence of 70% will be considered to be what is necessary to meet the objectives of the research both by subject diary and by bottle weight. Therefore, subjects who have an adherence of less than 70% will not be considered for the efficacy analysis, they will only enter the safety analysis.

6.5 Strategy to improve adherence

1. The Principal Investigator (PI) will sensitize the subject to the importance of the correct application of the research product (IP) to achieve the objectives of the study.
2. Direct questioning by the PI about the application of the IP.
3. Delivery of a printed calendar specifying the date of the visit and its activities.
4. Training in the filling and revision of the subject's diary.
5. If deemed necessary, text messages may be sent as reminders. The content of these messages must be previously approved by the REC.

7. Methods and procedures of the study

This study will be carried out in research centers previously evaluated by the sponsor. These centers will be institutions or establishments where health research is carried out that complies with current regulations.

7.1 From the research center

According to the capacities of the centers evaluated during the feasibility, the number of centers that will be included will be determined. It is suggested that there are 4 or more.

The research center will be responsible for forming a multidisciplinary research team to execute the clinical study according to protocol. It is their prerogative to design the organization and select the personnel who will perform the functions. However, it is the sponsor's need for the PI to be a specialist in Ophthalmology.

Any person who is designated, under their responsibility, a part of the study monitoring (co-investigator, sub-investigator, nurse, etc.) or a specific function of participation in the study (pharmacist, administrative assistant, study coordinator, etc.) must appear in the "Delegation of Responsibilities".

The competence and training of any person who has direct participation in the activities of the study must be verified prior to the performance of any activity related to the protocol. The above must be recorded and the documents that constitute evidence of this competence and/or training must be kept in the master file of the study. The competence and training of the personnel who have functions in the study, both at the central level and in the study centers, is the responsibility of the sponsor.

The sponsor must ensure that all study site personnel participating in the study are adequately trained on the study (research protocol, investigator's manual, amendments, standard operating procedures, etc.) and on the good practices of the study.

Clinical Internships of the International Conference on Harmonization (ICH), before the start of their participation in it. Training must be recorded in writing and those records must be filed in the master record of the study.

7.2 Clinical study registration

This clinical study will be registered by the sponsor in public clinical trial registries before its start (inclusion of the first patient): National Registry of Clinical Trials (RNEC) of the Federal Commission for the Protection against Sanitary Risks (COFEPRIS) and in a primary registry platform of the World

Health Organization (WHO). WHO Primary Registries meet specific criteria for content, quality and validity, accessibility, unique identification, technical capacity and administration. WHO Primary Registries meet the requirements of the International Committee of Medical Journal Editors (ICMJE).

7.3 Randomization

Randomization of subjects will be carried out using a computer-based assignment system. After signing the ICF, the patient will receive a patient number with which all their information will be encoded pseudonymity during collection and completely anonymous during analysis.

The generation will be carried out by a third party, authorized by Laboratorios Sophia, S.A. de C.V., through its electronic system. The information pertaining to this third party will be on file.

Although it is an open-label study, a secondary packaging masking will be performed.

The IP will be identified by means of labels in accordance with current and applicable regulations, which must contain at least:

- Sponsor's name, address, and phone number.
- Dosage form and route of administration.
- Batch number.
- Legend "For clinical studies only"
- Expiration date.

7.4 Outcome variables

7.4.1 Primary outcome of efficacy

- OSDI test score (ET: day 31).

7.4.2 Primary outcome of safety

- Incidence of AEs (ET: days 15 and 31).

7.4.3 Secondary outcome of efficacy

- Changes in the TFRT (ET: day 15 and 31).
- Corneal and conjunctival staining changes with lissamine green (ET:15 and 31).
- Corneal and conjunctival staining changes with fluorescein (ET: days 15 and 31).
- Conjunctival hyperemia changes (ET: day 15 and 31).
- Incidence of chemosis (ET: days 15 and 31).

7.4.4 Secondary outcome of safety

- Changes in the BCVA (ET: day 15 and 31).

- Changes in IOP (ET: day 15 and 31).

7.4.5 Definition of variables, methods and scales to be used for measurement

Variable	Type of variable	Unit (symbol)	Method of measurement	Normal value	Evaluation time	Test statistics
Primary outcome of efficacy						
OSDI	Quantitative discrete	Score	Questionnaire	< 13	BV and FV	ANOVA Student's t test*
Secondary outcome of efficacy						
TFRT with fluorescein	Quantitative continuous	Second(s)	Direct observation with slit lamp and cobalt blue filter	> 10s	BV, V1 and FV	ANOVA Student's t test*
Corneal and conjunctival staining with lissamine green	Categorical ordinal	Degrees	Direct observation with slit lamp, evaluated with Oxford's scale	0	BV, V1 and FV	Pearson's χ^2 or Fisher's exact test. McNemar's test*
Corneal and conjunctival staining with fluorescein	Categorical ordinal	Degrees	Direct observation with slit lamp, evaluated with Oxford's scale	0	BV, V1 and FV	Pearson's χ^2 or Fisher's exact test. McNemar's test*
Conjunctival hyperemia	Categorical ordinal	Grades (Efron)	Direct observation with slit lamp, evaluated with Efron's scale	0	BV, V1 and FV	Pearson's χ^2 or Fisher's exact test. McNemar's test*
Chemosis	Categorical nominal	Present/absent	Observation	Absent	BV, V1 and FV	Pearson's χ^2 or Fisher's exact test. McNemar's test*
Primary outcome of safety						
AE	Quantitative discrete	Number of Cases (N)	Count	0	BV, V1 and FV	ANOVA
AE(bis)	Categorical nominal	Present/absent (-)	Observation	Absent	BV, V1 and FV	Pearson's χ^2 or Fisher's exact test.
BCVA	Quantitative discrete	Fraction (-)	Snellen chart	1	BV, V1 and FV	ANOVA Student's t test*
IOP	Quantitative discrete	Number	Tonometry	≥ 10 and ≤ 21	V1 and FV	ANOVA Student's t test*

OSDI, ocular surface disease index; TFRT, tear film rupture time; AEs, adverse events; BCVA, better corrected visual acuity; IOP, intraocular pressure; ANOVA, Analysis of Variance; χ^2, Chi-square. *When applicable.
						

Table 3. Operational definition of variables

The variables, method, and scales for their measurement are described in detail below. They are in order according to Table 3.

7.4.5.1 OSDI Score

The OSDI is a validated and reliable instrument to measure the severity of dry eye, it has the necessary psychometric properties to be used as an outcome variable in clinical studies. [49] It consists of a questionnaire with 3 questions and 12 items, the answer is in frequency and offers 5 options from 4 (at all times) to 0 (at no time), questions 2 and 3 also contain the NA option. (See: 16.1) The OSDI score is calculated based on the following formula:

$$\text{OSDI} = \frac{D \times 25}{E}$$

Where:

D = sum of the points of the questions answered

E = number of items answered, those answered with NA are not counted as answered

The OSDI score will be recorded on the electronic Case Report Form (eCRF).

Management as AE: An increase of more than 40% in the value of the OSDI score at the basal visit should be reported and managed as an AE for lack of effectiveness.

7.4.5.2 Tear film rupture time

One of the first aspects of the tear film to change when there is an alteration to the ocular surface is its stability. In general, if the corneal or conjunctival surface is damaged, it is unlikely that a stable tear film can be maintained.

The most common method of assessing tear film stability is fluorescein evaluation of TFRT. Once the fluorescein has been instilled, the cobalt blue filter asks the patient not to blink after blinking 1 to 2 times. The fluorescein-colored precorneal layer will change to less fluorescent or non-fluorescent regions. The time that elapses from the last blink to the appearance of these regions is the TFRT. It will be reported in seconds, in the clinical record and in the eCRF.

Management as AE: a decrease in TFRT of more than 40% compared to baseline should be reported and managed as an AE due to lack of efficacy.

7.4.5.3 Corneal and conjunctival staining with fluorescein

A drop of topical anesthetic will be instilled in the bottom of the conjunctival sac, then a second drop will be applied to the tip of the fluorescein strip, allowing it to sit on the strip for 5 seconds to elute the dye, shaking off the excess at the end. A small contact of the strip is made with the conjunctiva at the fundus of the temporal sac, while the patient looks upwards, without damaging the conjunctiva. It will be graded according to the Oxford scale (See: 16.2). [50]

The PI will record in the file and the eCRF the grade awarded for fluorescein staining of DO and OS, respectively.

Management as AE: corneal stains that are equal to or greater than grade III will be considered as AEs.

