7.4.5.5 Conjunctival hyperemia

Conjunctival hyperemia is defined as the simplest reaction of the conjunctiva to a stimulus, with a red appearance secondary to vasodilation of the conjunctival vessels of variable intensity. You will graduate using the Efron scale (See 16.3). [51]

Management as AE: conjunctival hyperemia classified as grade 3 or higher will be considered as AE.

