7.4.5.9 Intraocular pressure

Intraocular pressure (IOP) is a measurement through tonometry, based mostly on the force required to flatten the cornea, or the degree of corneal indentation produced by a fixed force. Goldman tonometry is based on the Imbert-Fick principle. [53]

The tonometry will be performed, after instillation of the topical anesthetic, with fluorescein and the use of the cobalt blue filter (after the evaluation of the surface staining). 2 samples will be taken and the average will be calculated, which will be recorded in the clinical file. The average will be recorded in the eCRF.

Management as AE: intraocular pressure equal to or greater than 22 mm Hg should be reported and managed as AE.

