8.1.1 Meaning of adverse event

According to the ICH, an AE is any unfavorable medical appearance in a patient under clinical investigation who is administered a pharmaceutical product, regardless of causal attribution.

Therefore, an AE can be any of the following: any unfavorable and unintentional disease, symptom, or sign (including an abnormal laboratory finding) that is temporally related to the use of a medical product, whether or not it is considered related to such a product; any new illness or exacerbation of an existing disease (worsening of the nature, frequency, or severity of a known condition); relapse of an intermittent medical condition (e.g., headache) not present at baseline; any deterioration in a laboratory value or other clinical test (e.g., electrocardiogram [ECG], x-ray) that is related to symptoms or that results in a change in study treatment or concomitant treatment or discontinuation of study medication.

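### Fixed-threshold AE rules for corneal staining, hyperemia, chemosis and IOP, with no new-or-worsened rule in the analysis, let unchanged entry findings count in the primary safety outcome

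*Combined protocol and SAP*

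**What the plan says.** The protocol attaches an AE rule to most measured variables, and the rules are of two kinds.

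**Absolute, with no comparison to baseline:**
- Fluorescein staining (7.4.5.3): "corneal stains that are equal to or greater than grade III will be considered as AEs". Section 7.4.5.4 repeats the rule for lissamine green. Conjunctival staining has no AE rule.
- Hyperemia (7.4.5.5): "conjunctival hyperemia classified as grade 3 or higher will be considered as AE".
- Chemosis (7.4.5.6): its presence is an AE.
- IOP (7.4.5.9): "intraocular pressure equal to or greater than 22 mm Hg should be reported and managed as AE".

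**Written as a change:**
- OSDI (7.4.5.1): "An increase of more than 40% in the value of the OSDI score at the basal visit".
- TFRT (7.4.5.2): "a decrease in TFRT of more than 40% compared to baseline should be reported".
- BCVA (7.4.5.8): a loss of more than two Snellen lines.

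On entry, "Corneal staining with more than 5 sites" is one of three alternative qualifying signs (5.1.1). It is a floor with no ceiling. Section 5.2.1 excludes glaucoma, but not raised IOP alone, and sets no limit on staining grade or hyperemia.

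The primary safety outcome (7.4.2) is given as "Incidence of AEs (ET: days 15 and 31"). Table 3 gives AE evaluation times as the basal, first follow-up and final visits. Section 10.1.2 reports AEs in all randomized participants, and section 10.1.3 defines the safety set as all exposed subjects. Neither restricts the analysis to new or worsened events. Section 8.1.1 includes in its AE definition "any new illness or exacerbation of an existing disease", and section 3.2 sets the safety objective as unexpected AEs related to the product.

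**The concern.** Staining and hyperemia are features of the condition under study. A subject who enters with grade III corneal staining and still has it at day 15 meets the rule in 7.4.5.3, although nothing has happened since treatment began. The same holds for an IOP of 22 mmHg or more in a subject without glaucoma.

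The trial sets out to establish the ideal dosage (2.4.2 and 4.2), so AE incidence will be compared between dosages. Counting entry findings raises incidence in every arm for reasons unrelated to the product. It also makes the contrast between dosages depend on how often these signs are present at entry and how quickly they clear.

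**Working it through.** **Plan's own figures.** The documents give no expected AE incidence and no prevalence of these signs at entry. The only sample-size figure is for efficacy: 39 × 1.2 = 46.8, rounded to 47 per group, and 3 × 47 = 141. I use n = 47 below only as the group size.

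**Can an entry sign be counted?**
1. Can a subject enter at or over a threshold? Yes. Sections 5.1.1 and 5.2.1 set no upper limit on staining grade, hyperemia or IOP.
2. Does the sign then meet an AE rule? Yes, on the wording of 7.4.5.3 to 7.4.5.6 and 7.4.5.9.
3. Does the analysis remove it? No such rule appears in 7.4.2, Table 3 or 10.1.2 to 10.1.3.

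**Effect on the binary AE outcome if signs persist equally.** Let q be the share carrying a threshold sign at entry, the same in each arm and persisting. Let e be the true incidence of new or worsened AEs, independent of q.

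Observed incidence = q + (1 − q)e

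Observed difference = (1 − q)(e₂ − e₁)

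Illustration with assumed e₁ = 5% and e₂ = 25%. Power is two-sided at 0.05 with n = 47 per arm, normal approximation, using the unpooled and then the pooled null variance:

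| q | Observed | Difference (points) | Risk ratio | Power, unpooled | Power, pooled |
|---|---|---|---|---|---|
| 0 | 5.0% v 25.0% | 20 | 5.00 | 81% | 78% |
| 2% | 6.9% v 26.5% | 19.6 | 3.84 | 75% | 73% |
| 5% | 9.75% v 28.75% | 19 | 2.95 | 67% | 65% |
| 10% | 14.5% v 32.5% | 18 | 2.24 | 56% | 54% |
| 20% | 24.0% v 40.0% | 16 | 1.67 | 39% | 38% |
| 30% | 33.5% v 47.5% | 14 | 1.42 | 29% | 28% |

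With an assumed 10% v 30%, pooled power runs 68%, 58%, 49%, 36% and 28% at q = 0, 5%, 10%, 20% and 30%.

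**Effect if signs clear at different rates.** Let r be the share of entry signs that persist in an arm.

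Observed incidence = 1 − (1 − qr)(1 − e)

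Assume r = 90% and e = 5% at a lower dosage, and r = 40% and e = 15% at a higher one, so the true difference is 10 points:
- q = 10%: 13.55% v 18.4%, difference 4.85 points.
- q = 20%: 1 − 0.82 × 0.95 = 22.1% v 1 − 0.92 × 0.85 = 21.8%, difference −0.3 points.
- q = 30%: 30.65% v 25.2%, difference −5.45 points.

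Staining and hyperemia are also secondary efficacy outcomes (7.4.3), so unequal clearance is what an effective dosage would produce. The AE count would then mix efficacy with safety.

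**The case against.** Several parts of the protocol pull against counting entry signs:
- Section 7.4.5.7 defers to 8.1.1, which speaks of temporal relation to product use and of new or worsened conditions.
- Section 3.2 concerns only unexpected, related AEs, and causality is recorded for each event. A stable sign that predates exposure should not pass that filter.
- Section 7.4.5.7 leaves it to the investigator which findings of the ophthalmological evaluation are reported as AEs.
- Section 7.4.2 names days 15 and 31, not the basal visit.

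These soften the problem without removing it. Section 8.1.1 does not say that it overrides the variable-specific rules. The filter in 3.2 is not applied to the outcome in 7.4.2. The investigator's discretion covers procedures that are not study variables, so it reaches IOP at most. A sign that persists to day 15 meets the rule at day 15, wherever counting starts.

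Other objections stand. OSDI is capped at 32, need for stage 2 treatment is excluded, and so are other conditions that may interfere with interpretation. Carriage at entry could therefore be close to zero. There is no safety hypothesis and the trial is not sized for AEs. Table 3 also analyses AEs as a count by ANOVA: an equal expected addition to each arm leaves the mean difference unchanged and can only add variance. How a sign that persists across visits enters that count is not stated.

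**Conclusion.** The point holds as a gap between the recording rules and the analysed outcome: as written, an unchanged entry sign can be counted in the primary safety outcome. Its size cannot be derived from the documents. The factor (1 − q) is exact for the binary outcome only under equal persistence and independence of new events. All rates, carriage shares and power values above are illustrations.

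Four stronger readings are tempting but not supported:
- *The outcome counts the disease that qualified the subject.* Entry uses a site count, or TFRT alone, while the AE rule uses an Oxford grade. No mapping between them is given, and hyperemia, chemosis and IOP qualify nobody.
- *Any true dosage difference must shrink.* That needs equal persistence; with unequal clearance it could shrink, vanish or reverse.
- *AEs at the basal visit are necessarily counted before exposure.* Section 7.4.6.2 lists AE evaluation after product delivery and start of intervention, while section 6.3 starts application on D1. The timing is unclear.
- *Events first reported at the day-33 call are omitted.* The schedule in section 1.3 collects AEs at that call, and section 10.1 sets no day-31 cut-off. Omission is only an inference from the evaluation-time labels in 7.4.2 and Table 3.

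**What to change.** Leave every clinical threshold unchanged as a trigger for recording and follow-up. In section 10.1 and Table 3:
1. Define the analysed primary safety outcome as subjects with at least one AE that is new or worsened from the basal visit, arising after first application. State what counts as worsening for each sign, including IOP; that is for the sponsor's clinical team to specify.
2. List threshold findings present at entry separately, by arm.
3. Reconcile the AE evaluation times in 7.4.2 and Table 3 with the schedule in section 1.3 (basal visit and day-33 call), and state that events reported at the call are included.
4. Add the basal visit to the IOP line of Table 3, which now lists only the first follow-up and final visits although the schedule measures IOP at the basal visit.

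The cost is wording alone. Baseline staining, hyperemia, chemosis and IOP, and AEs at the safety call, are already collected under section 1.3.
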